PROTOCOL

Digital Self-management System to Support Blood Pressure Medication Adherence
21 Feb 2024

Basic Information		
Title of Study:	Digital Self-management System to Support Blood Pressure Medication Adherence	
Short Title:	Digital Technology to Support Adherence to Hypertension Medication	
Principal Investigator Name:	[name]	
Principal Investigator's Department/Unit:	College of Nursing/Biobehavioral Health Science	

1.0 Background (Limit 1,000 words):

Provide the scientific or scholarly background for the proposed Human Research. Discuss relevant prior experience or preliminary data (e.g., existing literature).

The prevalence of hypertension is estimated at $74.1\%^1$ for people ≥ 60 years, and uncontrolled hypertension is known to be a risk factor for cognitive decline. Addition adherence decreases the potential effects of hypertension on cognition. Medication adherence is defined as using medications as prescribed based on a regimen agreed upon between a patient and their provider and is crucial to medication benefit. People with mild cognitive impairment (PwMCI) are at risk of medication non-adherence.

Mild Cognitive Impairment (MCI) refers to impairment in one or more cognitive domains without fulfilling the diagnostic criteria for dementia. It is estimated that approximately 16–20% of people aged 65 or older have MCI and are known to be at risk of developing dementia. Given that the Food and Drug Administration (FDA) approved treatment of MCI is limited to intravenous infusion therapy, controlling co-morbid health conditions in PwMCI is critical to slow and possibly prevent progression to dementia. One of the strategies recommended by the World Health Organization (WHO) Global Action Plan on the public health response to dementia 2017– 2025 (WHO, 2017a)⁸ is to improve the management of hypertension, a common co-morbid condition in PwMCI. If it were possible to control vascular risk factors by adhering to prescribed hypertension medications, cognitive decline could be potentially prevented or modified in PwMCI.⁹

Although PwMCI are unimpaired in basic activities of daily living (ADLs) they experience functional impairment in complex instrumental activities of daily living (IADLs) such as medication self-management. Given that hypertension is asymptomatic and not associated with identifiable cues such as pain, it is easy for PwMCI to forget to take medications without regular reminders. The asymptomatic nature of hypertension also undermines the ability to sustain adherence because it is difficult to sense the improvement in health over time, and cues (e.g., pain) are not available to serve as reminders to take medications. Thus, an innovative intervention approach is needed to effectively support hypertension medication adherence.

An appropriate strategy for improving hypertension management for PwMCI is to leverage the advances in mobile health (mHealth) technology to foster medication self-management by tapping into preserved skill learning and procedural memory¹⁵⁻¹⁷ abilities. In terms of health monitoring technology, mobile applications (Apps) on smartphones hold strong potential for supporting self-management in older adults.¹⁸ The number of older adults using smartphones is rising and is currently 81% for adults aged 60-69 years^{19,20} making this a viable option for healthcare support. However, none to our knowledge have attempted to examine the use of health monitoring technology for medication adherence in PwMCI specifically tapping into preserved cognitive abilities such as skill learning and procedural memory.²¹⁻²³

In our previous work, we developed and tested the theory-based Multifaceted Prospective Memory Intervention (MPMI) aimed at improving hypertension medication adherence.²⁴ The MPMI is the only medication adherence intervention that has used prospective memory theory and research to guide the intervention development.^{25,26} The central goal of MPMI is to change medication-taking from an effortful process dependent on prospective memory to one more dependent on associative processes that are relatively preserved with aging. The MPMI was compared to an education-attention group among older adults aged ≥65 years. The MPMI resulted in a 35% increase in adherence to hypertension medications.²⁷ Our group has developed a mHealth technology called the Medication Education, Decision Support, Reminding, and Monitoring System (MEDSReM) to replicate the critical components of the MPMI. MEDSReM contains additional functions such as visualizations of adherence patterns over time and decision support specifically designed to meet the needs of older adults. Supported by an NIH grant, we have further refined the system to meet the needs of PwMCI through needs assessments, cognitive walk-throughs, heuristic evaluations, and iterative usability testing. This optimized system is called Medication Education, Decision Support, Reminding, and Monitoring System-Memory (MEDSReM-M)

MEDSReM-M system provides medication reminders consistent with the person's routines and prescribed frequency and is tailored to an activity (e.g., breakfast). Encouraging immediate action when reminded to take the prescribed medication at the correct time is a central component of MEDSReM-M as even a delay in the execution of a prospective memory intention as short as 5 seconds has been shown to lead to forgetting to do the intended task.²⁸ Monitoring is another critical component of prospective memory strategies, that is, creating the ability to check whether medications were taken as intended. PwMCI will be able to check and monitor whether they are taking their medication as intended using the MEDSReM-M system. Adherence is monitored over time, and users can see graphical representations of their adherence success. This type of feedback is motivating and can improve adherence in the long term.²⁹ The decision support tool improves proper adherence and reduces risk by responding to questions about whether to take a medication early. The system also offers education about hypertension and health management. The goal of the current study is to test the efficacy of MEDSReM-M system for PwMCI in a randomized controlled trial (RCT).

HSPP Use Only:
IRB Protocol for Human Subjects Research

References

Uncontrolled hypertension is known to be a risk factor for accelerated cognitive decline in older adults. It is well established that PwMCI with vascular risk factors including hypertension convert to dementia at a faster rate compared to peers with no vascular risks. Although blood pressure (BP) medications are good at reducing the negative results of uncontrolled hypertension, the benefits of BP medications may not be realized due to non-adherence (not taking medications as prescribed). An underlying deficit in prospective memory contributes to such medication nonadherence issues in PwMCI. We have developed a digital medication self-management system called Medication Education, Decision Support, Reminding, and Monitoring-Memory (MEDSReM-M) system based on the unique needs and preferences of PwMCI. This system is designed based on the theory-based Multifaceted Prospective Memory Intervention (MPMI), which significantly improved older adults' adherence to BP medications in a previous study. MEDSReM-M changes medication taking from a complex process of holding information in mind over time to a

customized, cue-driven simple process that is mostly preserved in PwMCI. The current project aims to test the benefits of using the MEDSReM-M system relative to a standardized educational intervention to support medication self-management in PwMCI.

3.0 Purpose:

Describe the purpose, specific aims, objectives, questions to be answered, hypotheses, and/or primary and secondary study endpoints of this Human Research protocol.

The purpose of this study is to examine the benefits of MEDSReM-M to support medication self-management in PwMCI.

Specific Aim: To determine the efficacy and identify predictors for the adoption of MEDSReM-M for PwMCI through a 4-month RCT relative to a standardized educational intervention.

Objective: To conduct a 4-month RCT to assess improvement in adherence, blood pressure (SBP), and technology acceptance in the MEDSReM-M group (N=50) relative to the standardized educational intervention group (N=50).

Hypothesis: We hypothesize that advances in technology can be leveraged in PwMCI to improve adherence by harnessing retained cognitive ability for skill learning and procedural memory.

Outcome: Completed RCT with identification of variables that inform improved adherence.

4.0 Funding Information:

Indicate all sources of funding for the project, including gift funds, departmental funds, or other internal funding. For each funder, list the name of the funder, and the institutional proposal number or award number you received from Sponsored Projects. eIRB tip: For externally funded projects, the institutional proposal or award number provided must be linked in the "Study Funding Sources" section in eIRB.

☐ No Funding	
☑ Federal Funding, including flow-through	Name of funding source:
federal funding (i.e., NIH, NSF, DoD, etc.)	National Institute of Nursing Research/NIH
	Institutional Proposal or Award Number:
	019618-00001
	eDoc # (for multi-site projects):
☐ Industry Funding	Name of funding source:
	Institutional Proposal or Award Number:
	eDoc #:
☐ Foundation Funding	Name of funding source:
	Institutional Proposal or Award Number:
☐ Department Funding	Name of funding source:

☐ Gift Funding	Name of funding source:
☑ Other	Name of funding source:

5.0 Resources Available to Conduct the Human Research:

Describe the resources (facilities, time, emergency resources, etc.) available to recruit, consent, conduct study procedures, and analyze data.

This multisite study involves the University of Arizona and the University of Illinois Urbana-Champaign. Potential participants for the proposed research will be identified through multiple avenues.

Available resources for potential recruitment: Recruitment will occur at varying sites in Arizona and Illinois with established partnerships with a variety of medical and community-based organizations. Participants will be recruited from neighborhood centers, senior living communities, area senior centers, and meal sites, which provide access to a diverse population of older adults in terms of age, sex, ethnicity, religion, education, and economic status. [name] gives talks at health-focused events, such as a public lecture series offered at area hospitals and community health fairs, and these events have proven to be valuable sources of potential participants. As in previous recruitment successes, the research team will be present in person at these sites and events to offer blood pressure screenings to meet potential participants and identify those who may be eligible for participation. People who are interested in hearing about the study will be asked for contact information through the encounter form (located in the appendix). The research staff will follow up with the potential participants ideally the next day, for formal recruitment into the study. Additionally, we will identify potential participants through local geriatric, cardiovascular, and primary care providers caring for older adults with hypertension who agree to display our recruitment brochures in their clinics (please see an example flyer for the language that will be used in flyers advertising the study). An ad in local newspapers will be used to reach older people not associated with sites or events using the same language as in the flyer. The print materials will contain both email and phone contacts of the project team so that participants may use either method with which they are most comfortable.

At Arizona, Banner University Medical Center, El Rio, Tucson Medical Center are potential recruitment options for this study. We will use the same language from the flyer and the emails found in the appendices to recruit prospective participants for this research study.

We will also use email to existing registries of people who have agreed to be contacted for potential participation in research studies. For example, [name] has an ongoing registry among the older adult community in southern Arizona.

We will seek site permission prior to recruitment activities.

At Illinois, participants will be recruited through [name] laboratory registry of PwMCI; Carle Neuroscience Institute, a recruitment site; and independent living seniors supported by CJE Senior Life in Chicago. [name] has a registry of PwMCI who are interested in participating in research studies. The MCI registry was developed by [name] research affiliation and ongoing MCI studies with the Carle

Neuroscience Institute, which sees approximately 100 MCI patients per year. Also, participants will be recruited in partnership with community partners including CJE Senior Life, which supports about 20,000 older adults, including PwMCI, who live in independent living communities. Participants will also be recruited through various participant registries including the Technologies to Support Aging-in-Place for People with Long-Term Disabilities (TechSAge) Participant registry (UIUC IRB #20662), Illinois Health and Engagement through the Lifespan Project Registry (I-HELP) research registry (UIUC IRB #08524), and The Disability and Education Services (DRES) Research Registry (UIUC IRB #13731). Individuals have signed up for these registries because they have expressed an interest in being contacted to participate in research studies. None of these recruitment sites will be directly involved in conducting research activities.

The Site PI will ensure that recruitment, consent, and implementation of study protocol will be conducted by study personnel who have completed required human subjects training, Good Clinical Practice (GCP) certification, and Conflict of Interest (COI) review. Study staff will also adhere to standardized training in the study protocol. With participants' consent, audio and video (of the Zoom screening) recordings will be made of visits with participants and reviewed by the Site PI and project coordinator to ensure fidelity to protocol.

We are contracting with Ephibian, a local computer science and electrical engineering company. Ephibian serves as a technical resource to the research team linked to the MEDSReM-M system and will not directly interact with participants. Ephibian builds high-performance software solutions and for more than 25 years has served multiple audiences including the aging population; in particular, the Patient Reported Outcomes Consortia (http://c-path.org/programs/pro/). Ephibian helped develop the first version of MEDSReM and the advanced design of our MEDSReM-M system. They specifically built the system to protect the smartphone's local device information with encryption, protect all data transmissions, require pin entry for application access for additional user security, remove any data on user request or application uninstallation, and meet HIPAA security requirements.

6.0 Study Population:

6.1 Select all the categories of participants included in the research:

☐ Healthy adults	☐ Non-English-speaking subjects
⊠ Non-healthy adults	☐ UA staff/faculty
☐ Children (under 18 years old) *	☐ UA students
☐ Pregnant women, neonates, and/or fetuses*	☐ Banner employees
☐ Prisoners*	☐ Refugees
☐ Native Americans, Alaskan Native, and Indigenous Populations*	☑ Other – please explain: PwMCI have only mild problems with cognition. They can make
☐ Adults unable to consent (i.e., cognitively impaired adults) *	independent decisions without needing assistance and are capable of providing informed consent.

6.2 For each of the above selected categories, describe the inclusion and exclusion criteria. Indicate age range, gender, and ethnicity.

PwMCI will meet the following general inclusion criteria: i) 60 years or older, ii) community-dwelling, iii) fluent in English, iv) have adequate self-reported visual and hearing ability to interact with others and with the smartphone, v) self-reported memory problems, (vi) the Modified Telephone Interview for Cognitive Status (TICS-M)¹ score between 27-37, vii) self-managing at least one antihypertension medication, viii) no diagnosis of dementia or other neurological disorders such as stroke, traumatic brain injury (TBI), and Parkinson's disease, ix) no major history of depression or other mental health diagnoses, and x) use a smartphone. Participants who do not meet these general inclusion criteria will be excluded.

Participants who meet general eligibility criteria and express interest in enrolling will be scheduled for a video screening. Electronic informed consent will be obtained from all participants using REDCap. After providing informed consent, participants will complete a background questionnaire. The Montreal Cognitive Assessment (MoCA)² will be administered to assess global cognition. The Geriatric Depression Scale (GDS)³ will be administered to screen for elevated depressive symptoms. Participants with MoCA cut-off scores between 20 to 26 will be invited to participate in the study. If they agree to participate, they will be scheduled for in-person consenting for the RCT and baseline assessment. If a participant does not qualify or prefers not to participate despite being eligible, they will be thanked for their participation. The session will last approximately 45 minutes. All participants regardless of eligibility will be paid \$15 for the video screening session.

Participants will not be excluded based on gender or ethnicity. Both women and men will be included, and both groups will be equally targeted for recruitment into the RCT. This project will include all potential participants regardless of their racial/ethnic background, limited only by the available population.

- 3. Yesavage JA, et al. Development and validation of a Geriatric Depression Screening Scale: A preliminary report. Journal of Psychiatric Research 1982; 17(1): 37-49.
 - 6.3 Describe the total number of subjects to be enrolled locally under this IRB approval. If obtaining specimens, specify the maximum number of specimens needed for this project.

A total of 100 PwMCI will be recruited. There will be two treatment arms: N=50 in the MEDSReM-M intervention group, which will be henceforth referred to as MEDManage-S, and N=50 in the standardized educational group, which will be henceforth referred to as the MEDManage-P. This is a multi-site project, and our local (University of Arizona) enrollment goal is n=60 participants. The research team at the University of Illinois Urbana-Champaign aims to enroll n=40 participants.

7.0 Recruitment Methods:

7 1	Salact the	mothods	ot beau	recruit individu	ıəle

⊠ Email	☐ Screening of the Electronic Medical
	Record (EMR)

☑ Face to face	☑ Social media
	☐ SONA System
☑ In person presentations	☑ TV, Radio, Print
☑ Online advertisements	☑ Other – please explain: research
☐ Phone calls	registries

7.2 Explain the recruitment process. Describe how potential subjects will be identified, where recruitment will take place, when recruitment will occur, and the methods that will be used to recruit individuals.

We will use our well-established multi-pronged recruitment strategies, which include word-of-mouth, email, and telephone scripts to members of established registries; flyers and brochures shared by community organizations and partners; advertisements in newspapers and newsletters; potential opportunities on the radio and television and personal visits to community events. All recruitment materials will be pre-approved by the IRB.

- Emails will be used to contact people who have expressed an interest in participating in research studies and are in an existing registry (as in the appendix).
- The same language used in the flyer will be used in flyers (as in the appendix), bookmarks, and brochures. We will work on the graphics to provide these additional means of advertising the study, but the language will not vary from what is shown on the flyer in the appendix.
- If a participant leaves a phone contact, we will call them and share information about the study.
- We will share information about the study at talks given for community centers. We will
 use the encounter forms if people are interested in learning more about the study.
- Social media: using the same language as in the flyer, we will publicize the study on social media, television and print.

At Illinois, participants will be recruited through [name] (Co-PI) laboratory registry of PwMCI, [name] (Co-investigator) Technologies to Support Aging-in-Place for People with Long-Term Disabilities (TechSAge) Participant registry (UIUC IRB #20662), the Illinois Health and Engagement through the Lifespan Project Registry (I-HELP) research registry (UIUC IRB #08524), and The Disability and Education Services (DRES) Research Registry (UIUC IRB #13731). Individuals have signed up for these registries because they have expressed an interest in being contacted to participate in research studies. Participants who are enrolled in these registries will be contacted about the study and inclusion criteria. These individuals will be emailed (see email drafts of the short announcement and study introduction in our recruitment materials) about the study and asked to contact our staff if interested in learning more about the study. Additionally, participants will be recruited from Carle Neuroscience Institute in collaboration with [name] (co-investigator), Staff Neurologist at Carle Hospital, and other local providers. Participants will also be recruited through community partners such as CJE Senior Life. CJE Senior Life supports about 20,000 older adults, including PwMCI, who live in independent living communities.

Phone Screening: Potential participants will undergo an initial phone screening to determine eligibility for the next step (the video screening). During this call, the research staff will gather information using the phone screening questionnaire and provide information about the study. The research staff will ask for the potential participant's verbal consent to retain information collected during the screening. If potential participants decline verbal consent, the research staff will not retain data from this call. TICS-M will be administered to screen for global cognition. Participants who score between 27-37 on TICS-M and meet the eligibility criteria will be invited to participate in a video screening. The research staff will clearly explain the time commitment, expectations for participation, and answer any questions the participant asks. If eligible individuals express interest in enrolling, the team will schedule an appointment for the video screening.

Video Screening: Electronic informed consent will be obtained from all participants using REDCap prior to conducting video screening. PwMCI will have no deficits in global cognitive functioning, as determined by TICS-M. Subtle cognitive changes observed in these individuals do not impact their ability to provide informed consent; therefore, no proxy consent will be required. After obtaining online informed consent, participants will complete a background questionnaire. The Montreal Cognitive Assessment (MoCA) will be administered to assess global cognition. The Geriatric Depression Scale (GDS) will be administered to screen for elevated depressive symptoms. Researchers will review and determine final eligibility for participation. Those who meet eligibility including a MoCA cut-off score between 20 to 26 will be invited to participate in the study. If they agree to participate, they will be scheduled for in-person consenting for the RCT and baseline assessment. If a participant does not qualify or prefers not to participate despite being eligible, they will be thanked for their participation. The session will last approximately 45 minutes. All participants regardless of eligibility will be paid \$15 for the video screening session.

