Phone Screening: Phone screening will not be recorded. Formal recruitment will be completed via phone to ensure privacy and individual attention. The research staff will follow up with interested potential participants who have shared their telephone contact information, ideally the next day for recruitment into the study. The team will document all attempts to contact potential participants and will vary the day and time of contact attempts if the person is not reachable on the first attempt. During the screening call, verbal consent will first be obtained prior to asking questions to determine eligibility. The research staff will confirm that participants meet the following criteria: i) 60 years or older, ii) community-dwelling (that is not in an assisted living situation) iii) able to speak and read English, iv) have adequate self-reported visual and hearing ability to interact with others and the smartphone, v) self-reported memory problems, vi) managing at least one hypertension medication, vii) no self-reported diagnosis of dementia or other neurological disorder such as stroke, TBI, and Parkinson's disease, viii) no major history of depression or other mental health diagnoses, and ix) experience using a smartphone. If participants are eligible, they will complete the Modified Telephone Interview for Cognitive Status (TICS-m); eligible participants will score between 27-37. The research staff will clearly explain the time commitment, expectations for participation, and answer any questions the participant asks. If the person expresses interest in enrolling and is eligible, the participant will be scheduled for a video screening. The phone screening will span approximately 5-15 minutes.

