Video Screening: After providing electronic informed consent, participants will complete video screening. The video screening will be recorded. Video screening will include the Montreal Cognitive Assessment (MoCA), and Geriatric Depression Scale (GDS). Participants will also complete questionnaires on demographic information (age, gender, education, race/ethnicity, income, living situation, comorbidities, and medications), nature of support received by a caregiver, and health status. Responses to these items can be entered by the data collector directly into an electronic file. Participants with MoCA cut-off scores between 20 to 26 will be invited to participate in the study and complete an in-person baseline assessment. If they agree to participate, they will be scheduled for in-person consent for the RCT and baseline assessment. If a participant does not qualify or prefers not to participate despite being eligible, they will be thanked for their participation. The video session will last approximately 45 minutes. All participants regardless of eligibility will be paid \$15 for the video screening session.

Visit 1 Baseline Assessment: The baseline assessment will be scheduled within three months of the video screening. Informed consent will be completed in-person for the RCT in a private space by research staff who are trained in Human Subjects Protection before study procedures are administered. Upper arm circumference will be measured to determine the appropriate-sized blood pressure monitor cuff. To obtain blood pressure readings (BP), the research staff will use the Omron 3 Series Upper Arm Blood Pressure Monitor (FDA approval: https://fda.report/PMN/K062027), if participants require an XL BP cuff. Utilizing the 2017 American College of Cardiology/American Heart Association's guidelines for home blood pressure measurement (HBPM), BP readings will be obtained both standing and sitting. If a problem is detected

during the visit, for example an elevated BP (>180 mm Hg systolic or 110 mm Hg diastolic), or an unusually low BP reading (<90 systolic), or BP that drops more than 20 mmHg when standing, the research staff will encourage participants to contact their primary care provider.

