Randomization Process: The randomization process is designed to achieve the appropriate generation of the random allocation sequence and concealment of the allocation sequence. A researcher who is not involved in phone screening, video screening, or informed consent will generate the randomization list prior to the screening of the first person for the randomized, controlled trial. The randomization list will use computer-generated random numbers and will use block randomization. The block size will vary randomly between 4 and 6. Research personnel who perform phone screening, video screening, informed consent, or assessments will not be able to access the randomization list.

For participants randomized into the MEDManage-S intervention arm (MEDSReM-M app + Standardized Education via the portal; n=50), research staff will walk participants in this group, through the process of downloading the MEDSReM-M app to their phones and accessing the portal. The portal has standardized information on hypertension and medications and links to vetted resources (e.g., the American Heart Association, National Heart, Lung and Blood Institute pages) for laypersons on their phones. Participants in the MEDManage-P control arm (Standardized Education Group without the MEDSReM-M app; n=50) will receive education on hypertension and antihypertensive medications and the link to the participant portal that has the standardized information on hypertension and medications websites resources that have been vetted (e.g., the American Heart Association, National Heart, Lung and Blood Institute pages) for laypersons. The research staff will walk them through the process of accessing the portal on their phones. Participants in both groups will be recorded and checked for consistency. If drift from the initial intervention protocol is detected, the project coordinator will make a note of the session in the participant file on REDCap. The coordinator will meet with the study staff to review the audio recording, discuss areas in which the intervention strayed from the protocol, and conduct retraining. Please see screenshots of the app added to the appendix.

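### No rule keeps two members of one household out of opposite arms, so a control may live with the app; the dilution is probably small and the remedy costs one eligibility line

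*Protocol*

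**What the plan says.** **Eligibility.** Section 6.2 of the protocol begins "PwMCI will meet the following general inclusion criteria: i) 60 years or older, ii) community-dwelling" and runs through ten items: age, residence, language, senses, memory complaint, TICS-M, medication, two diagnostic exclusions and smartphone use. None concerns other members of the household. The only exclusion attached to the list is "Participants who do not meet these general inclusion criteria will be excluded", so a second household member who meets the items is admitted. The nine-item phone-screen list in 10.2 defines residence as "community-dwelling (that is not in an assisted living situation" and also has no household item.

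**Living situation.** It is collected at the phone screen (8.3) and again at the video screen (10.2), within "age, gender, education, race/ethnicity, income, living situation, comorbidities, and medications". Beyond the residence criterion, no eligibility or allocation rule uses it.

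**Recruitment.** Section 5.0 states "Participants will be recruited from neighborhood centers, senior living communities, area senior centers, and meal sites" and names a partner organisation serving older adults "who live in independent living communities". Section 7.2 describes "multi-pronged recruitment strategies, which include word-of-mouth, email, and telephone scripts to members of established registries", together with talks and community events.

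**Allocation and arms.** The Randomization Process in 10.2 describes one blocked list of individuals and no household unit. Both arms get the education portal and a home blood pressure monitor (10.2). The intervention arm adds the app. Section 12.1 adds a pillbox that all intervention participants are given and encouraged to use. Section 1.0 explains that reminders follow the user's routine and are attached to an activity, with breakfast as the example. The protocol does not address contamination between arms.

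**The concern.** The comparison rests almost entirely on the app, because education is common to both arms. The app works by linking medication-taking to a daily event. People who live together may share such events, so a control whose partner has the app may notice the prompt, follow the partner's routine or copy the use of a pillbox. Any transfer raises adherence among controls and shrinks the contrast, against the trial's own hypothesis.

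Eligibility and the unit of allocation are protocol matters. An analysis plan could model the correlation between partners, but it cannot remove exposure that has already happened.

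**Working it through.** The protocol gives no alpha, power, effect size, count of couples or contamination allowance, so there is no stated figure to reproduce. The check bounds the size from its prevalence figures plus labelled assumptions.

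**Inputs from section 1.0:** hypertension 74.1% (age 60 and over); MCI 16–20% (age 65 and over); smartphone use 81% (age 60–69). **From 6.3:** 100 participants, 50 per arm.

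**Assumptions:** the three prevalences are independent; 30–60% of participants live with another older adult; uptake and transfer as given in each step.

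1. Housemate meets the three criteria: 0.741 × 0.16 × 0.81 = 0.096, up to 0.741 × 0.20 × 0.81 = 0.120.

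2. Chance that a first participant has an eligible housemate: q = 0.30 × 0.096 = 0.029, up to q = 0.60 × 0.120 = 0.072.

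3. Couples among 100 participants if every eligible housemate joins: 100q/(1 + q) = 2.8 to 6.7.

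4. With 25–50% uptake, q becomes 0.25 × 0.0288 = 0.0072, up to 0.50 × 0.0720 = 0.0360. Couples: 0.7 to 3.5.

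5. Couples split between arms. Independent allocation splits 50%. For two adjacent places on a list with blocks of 4 and 6 (equally likely), the figure is (3 × 2/3 + 5 × 0.6 + 2 × 0.5)/10 = 60%. Split couples: 0.7 × 0.5 = 0.4, up to 3.5 × 0.6 = 2.1.

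6. Each split couple exposes one control. If a fraction c of controls receives a share t of the app's effect, the contrast becomes δ(1 − c·t). With t = 0.5, dilution runs from 0.36 × 0.5/50 = 0.4% to 2.1 × 0.5/50 = 2.1%.

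7. Power, for illustration only. Assume 80% power at 50 per arm and two-sided 0.05, which corresponds to a standardised difference of 0.56. A 2% dilution gives 0.56 × 0.98 = 0.549 and power of about 78%. Five couples, with a 60% split and 50–100% transfer, give 75–78%.

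The arithmetic leaves out several criteria that lower the count: drug treatment rather than a hypertension diagnosis, self-reported memory problems, TICS-M 27–37, MoCA 20–26, the neurological and mental-health exclusions, and English. Independence may err in either direction.

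**The case against.** The protocol states nothing wrongly here. It lacks an optional safeguard, in a trial that randomizes individuals. No section mentions couples, and several recruitment sources reach people singly: the MCI and other research registries, the neuroscience institute and clinic brochures. The app is installed on the participant's own phone (10.2) behind a PIN (5.0). A shared prompt needs both partners to have the same dosing time and cue. The adherence graphs and decision support would not pass to someone who merely overhears a reminder. All of this stands as a limit on size. It does not close the gap, because a PIN does not hide a reminder, a routine or a pillbox from a partner.

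A reader might infer four stronger points that the document does not support:

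- **Dilution of 3–8%.** This follows only if every eligible housemate joins, the control receives the whole app effect and 60% of couples are split (1.7 to 4.0 split couples over 50 controls). It is a stack of worst cases, not an estimate.
- **Block size as a cause.** The text "The block size will vary randomly between 4 and 6" adds at most 10 percentage points to the chance of a split. On 3–7 couples that is 0.3–0.7 of one couple. It needs adjacent places on one list and fades to 57% at a gap of two places and 52% at four. Allocation takes place at Visit 2, four weeks after a baseline that may itself fall up to three months after video screening, and the protocol does not say whether the sites share a list.
- **Confusion between two MEMS bottles.** At Visit 1 each participant labels the container with their own name and medication details, and staff check the label (10.2).
- **An analysis that ignores correlated partners.** The protocol gives no model for the main comparison, only intention to treat (15.2) and correlations with sex (8.1). That question belongs to the analysis plan, which is not at hand.

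**Conclusion.** The gap is real. Nothing in 6.2, the phone screen or the randomization text prevents two members of one household from enrolling in opposite arms, and the resulting bias would run toward no difference. Its size is probably small: about 3–7 couples as a ceiling on uptake under the stated assumptions, and roughly 0.4–2% dilution with 25–50% uptake and 50% transfer. The household share, the uptake and the transfer are all assumptions, because the protocol gives none of them. The case for acting rests on the known direction of the bias and the very low cost of preventing it, not on a threat to the trial's conclusion. Label: cheap improvement.

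**What to change.** Add one criterion to 6.2 and to the phone-screen list in 10.2: *No other member of the household is or has been enrolled in this trial.* The first person to consent takes the place. Check it with one question at the phone screen, where living situation is already asked. The cost is one line, one question and a few otherwise eligible partners who are not enrolled.

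If losing those partners is unwelcome, household members could be assigned to the same arm, with the pairing accounted for in the analysis. That also closes the gap, at the price of a small clustering allowance.
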